2. CD4
3. CD8
4. FoxP3 (SP97)
5. Anti PDL-1 (E1L3N)

Modifications to the immune markers may be made depending on emerging evidence.

6 ETHICAL AND REGULATORY REQUIREMENTS

6.1 Ethical conduct of the study

This trial will be conducted in compliance with this protocol, Good Clinical Practice guidelines (eg, ICH E6: Good Clinical Practice or Singapore Guideline for Good Clinical Practice [SGGCP]), and applicable national and local regulatory requirements.

The site Principal Investigator shall ensure that personnel involved in the conduct of this study are qualified by education, training, and experience to perform their respective tasks. The site Principal Investigator has ultimate responsibility for trial conduct at the site.

The study will be performed in accordance with ethical principles that have their origin in the Declaration of Helsinki and are consistent with ICH/Good Clinical Practice, and applicable regulatory requirements.

6.2 Subject data protection

Subjects will be assigned unique code numbers and will not be identified by name. Subject confidentiality is held strictly in trust by the participating Investigators, their staff, the sponsor(s), and their agents. This confidentiality extends to genetic and biological sample tests, in addition to the clinical information relating to participating subjects.

The sponsor will not provide individual genotype results to subjects, any insurance company, any employer, their family members, general physician or any other third party, unless required to do so by law.

Extra precautions are taken to preserve confidentiality and prevent genetic data being linked to the identity of the subject. In exceptional circumstances, however, certain study staff might see both the genetic data and the personal identifiers of a subject. For example, in the case of a medical emergency, the medical monitor or an Investigator might know a subject's identity and also have access to his or her genetic data. Also, Regulatory authorities may require access to the relevant files, though the subject's medical information and the genetic files would remain physically separate.

The study protocol, documentation, data, and all other information generated will be held in strict confidence. No information concerning the study or the data will be released to any unauthorized third party without prior written approval of the sponsor.

6.3 Ethics and regulatory review

Before study initiation, the Investigator must have written and dated approval/favorable opinion from the IRB/IEC for the protocol, consent form, subject recruitment materials/process (eg, advertisements), and any other written information to be provided to prospective subjects. The Investigator should also provide the IRB/IEC with a copy of the product labelling information to be provided to prospective subjects, along with any updates.

The Investigator should provide the IRB/IEC with reports, updates, and other information (eg, expedited safety reports, amendments, and administrative letters) according to local and national regulatory requirements or institution procedures.

6.4 Informed consent

Investigators must ensure that subjects are clearly and fully informed about the purpose, potential risks, and other critical issues regarding this clinical study for which they are volunteering to participate.

Before any study procedures are performed, potential subjects will have the outline of the study described to them, and they will be given a written informed consent document to read. If they consent to participate in the study, they will indicate that consent by signing and dating the informed consent document in the presence of study personnel. Any subject who signs the consent form will be considered a "screened" subject.

6.5 Changes to the protocol and informed consent form

Should amendments to the protocol and/or informed consent document be required, the amendments will be written by the sponsor and provided to the Investigator for submission to

6.6 Protocol deviations

Protocol deviations (noncompliance with the clinical trial protocol, Good Clinical Practice (GCP), Manual of Procedures or requirements) will be noted in Site Monitoring reports. Of note, noncompliance may be either on the part of the participant, the site Investigator, or the study site staff. Sites are expected to develop and implement corrective actions promptly.

It is the responsibility of the site to use continuous vigilance to identify and report deviations. All deviations must be promptly reported to the sponsor or their designee.

All deviations from the protocol must be addressed in study subject source documents. Protocol deviations must be reported to the local IRB/IEC per local guidelines. The site PI/study staff is responsible for knowing and adhering to their IRB/IEC requirements.

6.7 Publication policy

Dissemination of preliminary information can adversely affect the objectivity of study data. For this reason, Investigators will not be allowed to perform subset analyses at any point before the conclusion of the study, and any data, other than safety data, cannot be used for publication or reporting outside of this study until the study is completed or discontinued by the sponsor/investigator.

7 STATISTICAL METHODS AND SAMPLE SIZE DETERMINATION

7.1 Statistical analyses and determination of sample size

Based upon current standard of care,³⁰ the median PFS (mPFS) in this population is estimated to be approximately 2 months, and a clinically relevant improvement with either of the proposed maintenance treatments would be to an mPFS of 4 months. In both arms of the study, it is proposed to test a null hypothesis of an mPFS of 2 months against an alternative hypothesis of an mPFS of 4 months. To test this hypothesis, assuming an exponential PFS distribution, use of an exponential MLE test, a two-sided significance level of 5% and a power of 90%, 25 subjects are required per arm. To allow for a drop-out rate of approximately 20%, the sample size per arm will be inflated to 30 subjects, for a total of 60 subjects.

Comparison between the two treatment arms will be performed as an exploratory analysis.

The number of subjects that will agree to participate in the genetic research is unknown. It is therefore not possible to establish whether sufficient data will be collected to allow a formal statistical evaluation or whether only descriptive statistics will be generated. A statistical analysis plan will be prepared where appropriate.

7.2 Safety data review committee

Accruing vital status, progression, and safety data will be reviewed by the committee comprising the Dora Study Chair, Study Co-Chair and Correlative Science Chair; one of the Study Chairs will serve as the bi-monthly committee meeting leader. The DCRI statistician will serve as the meeting secretary and will provide agreed-upon statistical reports in advance of the committee meeting. The Safety Data Review Committee's primary goal is to determine if there is a clear

early difference between the Arms A and B in terms of safety, efficacy, or risk-benefit. The Safety Data Review Committee may invite opinions from the study site investigators, intermittently, and will consider stopping either one, or both, arms if the safety profile is unacceptable. The committee will meet together and review rates of deaths, SAEs, and progressions approximately every 2 months until all subjects have been accrued. A written committee charter will provide guidance regarding meeting conduct; the DCRI statistician and the meeting Chair will jointly prepare summary minutes from each meeting and circulate for review by the committee members.

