1.5.3 Rationale for dose of olaparib in combination with durvalumab

A recent phase 1 study presented results for durvalumab therapy in combination with olaparib for ovarian cancer and TNBC, at the American Society of Clinical Oncology (ASCO) 2016. 10 ovarian cancer and 2 TNBC patients were included. Grade 3/4 adverse events included lymphopenia (2/12) and anemia (1/12). 1 PR (6 months) and 5 SD \geq 4 months were seen in 9 evaluable patients, yielding a 67% disease control rate (DCR).³³

Dosage of olaparib tablets 300 mg bid along with durvalumab 1500 mg Q4W was tolerated and efficacious in these patients who did not possess germline BRCA mutations, and is the recommended phase 2 dose (RP2D) employed in this study.³³

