Following randomization, subjects will discontinue platinum chemotherapy and receive either olaparib tablets or olaparib in combination with durvalumab. Study treatment should commence following resolution of chemotherapy toxicities to CTCAE grade 2 or less and no more than 4 weeks after last dose of chemotherapy. Study treatment will continue until disease progression, intolerable toxicity, elective withdrawal from the study, or study completion or termination. Upon treatment discontinuation, subjects will be followed every 2 months for survival.

Safety will be evaluated on an ongoing basis in this study through the monitoring of all serious and non-serious adverse events, graded according to National Cancer Institute Common Terminology Criteria for Adverse Events, Version 4.03 (NCI CTCAEv4.03).

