5.3 Definition of adverse events of special interest (AESI)

An adverse event of special interest (AESI) is one of scientific and medical interest specific to understanding of the Investigational Product and may require close monitoring and rapid communication by the investigator to the sponsor. An AESI may be serious or non-serious. The rapid reporting of AESIs allows ongoing surveillance of these events in order to characterize and understand them in association with the use of this investigational product.

AESIs for durvalumab include but are not limited to events with a potential inflammatory or immune-mediated mechanism and which may require more frequent monitoring and/or interventions such as steroids, immunosuppressants and/or hormone replacement therapy. These AESIs are being closely monitored in clinical studies with durvalumab monotherapy and combination therapy. An immune-related adverse event (irAE) is defined as an adverse event that is associated with drug exposure and is consistent with an immune-mediated mechanism of action and where there is no clear alternate aetiology. Serologic, immunologic, and histologic (biopsy) data, as appropriate, should be used to support an irAE diagnosis. Appropriate efforts should be made to rule out neoplastic, infectious, metabolic, toxin, or other etiologic causes of the irAE.

Only AESIs meeting serious criteria will be reported during the Extension period.

If the Investigator has any questions in regards to an adverse event (AE) being an irAE, the Investigator should promptly contact the Study Chair.

Criteria for Hy's Law (FDA Guidance 2009)

- The drug causes hepatocellular injury, generally shown by a higher incidence of 3-fold or greater elevations above the ULN of ALT or AST than the (non-hepatotoxic) control drug or placebo
- Among trial subjects showing such aminotransferase elevations, often with aminotransferases much greater than 3 x ULN, one or more also show elevation of serum total bilirubin to >2 x ULN, without initial findings of cholestasis (elevated serum alkaline phosphatase).
- No other reason can be found to explain the combination of increased aminotransferases and total bilirubin, such as viral hepatitis A, B, or C; pre-existing or acute liver disease; or another drug capable of causing the observed injury.

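### Section 7.2 ends the periodic by-arm safety review when accrual is complete, although treatment in both arms and SAE collection continue beyond that point

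*Combined protocol and SAP*

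**What the plan says.** Section 7.2 sets up a single committee made up of the study's chairs. Its main goal is to detect a clear "early difference between the Arms A and B in terms of safety, efficacy, or risk-benefit", and it "will consider stopping either one, or both, arms if the safety profile is unacceptable". On timing and content, it will "review rates of deaths, SAEs, and progressions approximately every 2 months until all subjects have been accrued". No other monitoring board, and no later aggregate review, appears in the documents.

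The same section also describes the remit more broadly: "Accruing vital status, progression, and safety data will be reviewed by the committee". The DCRI statistician "will provide agreed-upon statistical reports in advance of the committee meeting", but the content of those reports is not given. A written charter is mentioned as guidance on how meetings are run. It is not among the documents.

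Elsewhere in the protocol:

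- **Section 3.1:** study treatment has no fixed maximum duration. It ends with progression, intolerable toxicity, withdrawal, or the end of the study. The section adds: "Safety will be evaluated on an ongoing basis in this study through the monitoring of all serious and non-serious adverse events".
- **Section 5.4.1:** in the Extension period SAEs are collected through 30 days after the last dose of either drug, or until another anticancer therapy starts.
- **Sections 5.3 and 5.4:** in the Extension period only SAEs, and AESIs that are serious, are reported.

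**The concern.** The end of review is tied to enrolment, whereas risk follows exposure. A subject randomized last may contribute no on-treatment data to any scheduled review. Subjects enrolled earlier who are still on drug at accrual close have their later toxicity compared between arms at no planned point. The SAE data for that period will exist, but the plan assigns nobody to read them in aggregate.

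This matters more than usual for two reasons given in the protocol. First, experience with the combination is thin: in the phase 1 study behind the dose (section 1.5.3), "10 ovarian cancer and 2 TNBC patients were included". Second, section 1.1.4 reports secondary MDS or acute myeloid leukemia after olaparib treatment lasting from under 6 months to over 2 years, and both arms receive olaparib.

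A smaller question concerns content. The rates listed in section 7.2 are narrower than the safety data promised in its opening sentence. Section 5.3 says that AESIs may be non-serious and explains why they are reported quickly: "The rapid reporting of AESIs allows ongoing surveillance of these events". A reader cannot tell whether non-serious AESIs or grade 3-4 AEs reach the committee by arm.

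**Working it through.** The plan gives no figure for exposure at accrual close, so there is none to reproduce. The check sizes the gap.

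**Inputs from the documents**

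- 60 subjects, 30 per arm (section 7.1), allocated 1:1 (section 3.1).
- Median PFS of 2 months under the null and 4 months under the alternative, with an exponential distribution (section 7.1).

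**Assumptions**

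- Accrual is uniform over A months. The documents give no accrual length, so A = 12, 24 and 36 are shown.
- Time on treatment is exponential, with PFS as a proxy.
- The last review coincides with accrual close.

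**Formulas**

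- Mean time on treatment: m = median / ln 2. This gives 4 / 0.693 = 5.77 months, or 2 / 0.693 = 2.89 months.
- Expected subjects on treatment at close: N_on = (60 / A) × m × (1 − exp(−A/m)).
- The exponential is memoryless, so each subject on treatment at close has a further m months expected. The share of treatment time after close is therefore (N_on × m) / (60 × m) = N_on / 60.

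**One case in full** (median 4, A = 12): (60/12) × 5.77 × (1 − exp(−12/5.77)) = 5 × 5.77 × 0.875 = 25.2 subjects, and 25.2 / 60 = 42%.

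| Accrual A (months) | Median 4: on treatment at close | Share of treatment time after close | Median 2: on treatment at close | Share of treatment time after close |
|---|---|---|---|---|
| 12 | 25.2 | 42% | 14.2 | 24% |
| 24 | 14.2 | 24% | 7.2 | 12% |
| 36 | 9.6 | 16% | 4.8 | 8% |

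These counts cover both arms. With 1:1 allocation and the same median in each arm, the combination arm has half: 4.8 to 12.6 subjects at a 4-month median and 2.4 to 7.1 at a 2-month median.

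Faster accrual widens the gap. At A = 6 months the model gives 37.3 of 60 (62%) at a 4-month median and 25.2 of 60 (42%) at a 2-month median.

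**Limits of the proxy.** Withdrawal for toxicity or other drop-out before progression would shorten time on treatment and lower these figures. Treatment continued while progression is being confirmed (section 4.8), or beyond progression after consultation (section 4.3), would raise them.

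**The case against.** The strongest reply is that safety oversight does not stop at accrual close. SAEs are still reported within 1 business day (section 5.4), collected through 30 days after the last dose (section 5.4.1) and followed to resolution (section 5.5). The rules for interrupting or stopping treatment in individual subjects remain in force. Section 6.7 recognises that the sponsor/investigator can discontinue the study. Nothing in section 7.2 dissolves the committee, and its charter might provide for later meetings. Once enrolment is complete, no new subject can be exposed.

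Most of this stands, and it rules out several stronger readings that a reader might infer:

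- **That later exposure goes unreviewed.** It does not, because case-level reporting continues. What is missing is a planned aggregate review by arm.
- **That the committee sees only deaths, SAEs and progressions.** The opening sentence of section 7.2 is wider, and the report content is unspecified. The two sentences need reconciling, but they do not show that other events are withheld.
- **That section 3.1 is contradicted.** It describes monitoring across the trial and does not assign that task to this committee.
- **That the longest-treated subjects are missed.** Early enrollees are reviewed throughout accrual, and only their exposure after it falls outside. In the table above, 58% to 92% of treatment time comes before accrual closes.
- **That this is a problem of the combination arm.** It applies to both arms. MDS and cytopenias are described for olaparib, which both arms receive.
- **That MDS would escape the listed inputs.** Section 4.2.4 requires confirmed MDS to be reported as an SAE. At the under 1% in section 1.1.4, fewer than 0.6 cases would be expected in 60 subjects.

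The reply does not remove the stated end point. The charter is described only as guidance on meeting conduct, so it cannot be assumed to extend a limit written into the protocol. The sponsor's ability to discontinue the study does not supply a scheduled comparison by arm that would prompt such a decision.

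**Conclusion.** The concern holds in a limited form. As written, section 7.2 ends the periodic by-arm review at completion of accrual. It is carried out by the only committee described as able to consider stopping an arm. Treatment in both arms and SAE collection continue past that point with no planned aggregate review.

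Under uniform accrual over 12 to 36 months, with exponential time on treatment and PFS as its proxy, the exposure affected is about 16% to 42% of treatment time at a 4-month median (10 to 25 of 60 subjects) or 8% to 24% at a 2-month median (5 to 14 subjects). The accrual length is assumed, so the range matters more than any single value.

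This is a change worth making for subject safety. It does not affect the primary analysis or the sample size. Whether AESIs and grade 3-4 AEs are tabulated is a secondary point of clarification.

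**What to change.** In section 7.2, replace the end point of the periodic review (completion of accrual) with this: reviews continue until the last subject has completed study treatment and the 30-day safety follow-up. The interval may be lengthened after accrual. Deaths, SAEs, serious AESIs and progressions are already collected for that period and are enough for the reports. The charter should carry the same end point.

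As a clarification, align the opening sentence of section 7.2 with the rates listed later in that section. State whether AESIs, serious and non-serious, and grade 3-4 AEs are tabulated by arm for as long as they are collected. Non-serious events are not entered in the eCRF during the Extension period, so that part of the table would stop there. The amendment should say so.

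The cost is wording in the protocol and charter, plus a few more reports and meetings for the existing statistician and committee. No new members, subject visits or data collection are needed.

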9 APPENDICES

Appendix A : Schedule of Assessments

Extension period – please refer to sections 4.5.2 and 4.5.3 for data to be entered in eCRF.

SCHEDULE OF ASSESSMENTS					
Procedures	Screening ^p	Cycle 1 (q28)	Cycle 2 (q28) onwards	End of treatment	Follow-up
	Within 14 days	D1	D1 (+/- 3 days)	Within 30 days	Every 8 weeks (+/- 7 days)
Informed consent	X				
Inclusion/exclusion criteria check	X				
Demographics	X				
Past medical history including past cancer chemotherapy, radiotherapy and surgery	X				
Archival tumor tissue sample	X ^b				
Tumor assessment (CT or MRI) ^c	X		X ^d		X ^d
Complete physical examination	X	X	X	X	
Weight (with height at screening)	X	X	X		

Vital signs ^e	X	X ^e	X ^e	X	
AE and toxicities	X	X	X	X ^f	
Concomitant medications	X	X	X	X	
ECOG performance status	X	X	X	X	
Hematology ^g	X	X ⁿ	X	X	
Chemistry and electrolyte ^h	X	X ^o	X	X	
Liver panel (ALT/AST/Bilirubin) ⁱ	X	X ⁿ	X	X	
GFR assessment ^j	X	X ⁿ	X	X	
Pregnancy test ^k	X				
Buccal Swab for DNA analysis	X				
Biomarker blood tests ^l		X	X [after staging, at alternating Cycles 3,5,7, etc]	X	
Optional tumor biopsy ^m	X ^l			X ^m	
If CR/PR/SD:					
Randomization	X				
Olaparib		300 mg BID daily			
If randomized to combination arm:					
Durvalumab IV 1500 mg		X	X		
Survival assessment ⁿ					X ⁿ

NOTE: Results of standard-of-care tests or examinations performed prior to obtaining informed consent but within the screening window (Day-14 to Day -1) may be used for the study. Investigations, such as CT or MRI scans that have been performed as part of routine clinical practice to assess response to platinum, can be used as part of the screening process if performed within 28 days of first dose of study treatment. Screening assessments are to be performed within 14 days preceding cycle 1 day 1 unless otherwise noted. Except for cycle 1 day 1, all other study visits and assessments during the treatment period should be performed within +/- 3 days of the scheduled date. Study assessments may be delayed or moved ahead of the window to accommodate holidays, vacations and unforeseen delays. All assessments and procedures to be performed pre-dose unless otherwise specified.

^a The end of treatment visit should occur approximately 30 days after the last administration of olaparib or durvalumab

whichever is discontinued last, or until initiation of another therapeutic regimen.

^b Archival tissue (either formalin fixed paraffin embedded tumor specimens or a minimum of 10 unstained paraffin slides) must be available prior to entry into the study. In the absence of archival tissue, fresh tissue biopsy samples, excluding cytology and fine needle aspiration specimens are acceptable.

^c Tumor assessments performed according to RECIST version 1.1 The method used for a patient (CT or MRI) must be the same throughout the study.

^d Tumor assessment performed every 8 weeks starting on Days 21-28 of Cycle 2 and every 8 weeks (+/- 7 days) thereafter until documented disease progression. The results should be reviewed prior to dosing at the next cycle; tumor assessments should be performed <=7 days prior to continuation of study treatment on Day 1 of the subsequent cycle.

^e Includes heart rate, systolic and diastolic blood pressure whilst in a seated position, and temperature. On durvalumab dosing days, recorded prior to dosing and at the end of the infusion.

^f Patients with unresolved adverse events or serious adverse events will be followed until the event is resolved or stabilized, the patient is lost to follow-up or it has been determined that the study treatment or participation is not the cause of the event.

^g Includes RBC count, WBC count, WBC differential count (neutrophils, bands, lymphocytes, eosinophils, basophils, monocytes and other cells), absolute neutrophil count, hemoglobin, hematocrit and platelet count.

^h Includes sodium, potassium, chloride, bicarbonate urea, creatinine, calcium, phosphorus, magnesium, thyroid stimulating hormone (combination arm only), free triiodothyronine (T3) (combination arm only) and free thyroxine (T4) (combination arm only). See Appendix G for additional required tests for Korean sites only.

ⁱ Includes total bilirubin, total protein, albumin, AST, ALT and alkaline phosphatase.

^j As calculated by the Cockcroft-Gault formula.

^k For women of childbearing potential (including those who have had a tubal ligation). For all other women, documentation must be present in medical history confirming the patients is not of childbearing potential.

^l Biomarker blood specimens will be collected at visit C1D1, D1 after each staging cycle (C3D1, C5D1, C7D1 etc), and End of Treatment (EOT).

^m Tumor biopsy collection is optional for study participation if archival tissue is available. For patients who consent for tumor biopsy, this will be collected prior to treatment, and/or during interval of clinical response, at the time of progression and/or at the end of the study.

ⁿ Information about survival and subsequent anti-cancer therapies will be collected via telephone calls, patient medical records and or clinic visits approximately every 8 weeks until death, loss to follow-up, or study termination unless the patient requests to be withdrawn from follow-up; this request must be documented and signed by the investigator.

^o Where laboratory investigations have not been performed within the 7-day period prior to starting treatment, they must be repeated on day 1 of cycle.

^p ECG is required at screening for Korean sites only. See Appendix G.

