4.1.2 Screening Procedures

After written informed consent is obtained according to ICH GCP and local regulations, the subject’s eligibility for the study and baseline disease status will be evaluated. This will occur in a screening visit during which the following will be evaluated and documented within 14 days prior to first dose of study drug(s).

Investigations, such as CT or MRI scans that have been performed as part of routine clinical practice, can be used as part of the screening process if performed within 28 days of first dose of study treatment; however, no non-standard of care investigations or tests that are study specific and required for screening may be performed prior to signature of the informed consent form.

The following baseline information should be obtained within 28 days prior to randomization:

- Demographic data and medical history, including previous and current diseases and medications, and confirmation of all prior treatments for metastatic breast cancer, including platinum based treatment requirements of investigator choice.
- Check availability of archival tumor tissue sample or new tumor biopsy if archival tissue unavailable
- Baseline adverse events to document pre-existing toxicity from prior treatment (assessed using CTCAE v4.03)
- Tumor response to platinum based chemotherapy, evaluation by CT or MRI (as defined by investigator assessment)
- Physical examination including the assessment of height, weight, pulse rate and blood pressure and BMI.
- Eastern Cooperative Oncology Group (ECOG) performance status
- Blood tests^b
 - Full blood count (CBC with differential)
 - U&E: serum creatinine (SCr), urea, K+, Na+, glomerular filtration rate assessment
 - Liver function test: Bilirubin, ALP, AST/ALT, albumin
- Radiological investigations
 - CT or MRI scan to assess disease (thorax, abdomen and pelvis)
- Other tests
 - Pregnancy tests

See Appendix G for additional requirements for Korean sites only.

Where laboratory investigations have not been performed within the 7-day period prior to starting treatment, they must be repeated on day 1 of cycle 1.

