4.2.2 Olaparib

Olaparib (AZD 2281) (as film-coated tablet formulation) is intended for oral administration. The tablet monotherapy dose and the dose that will be used in this study is 300 mg bid taken continuously in 28 day cycles.

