4.5.2 Subsequent visits

Subsequent visits with study doctor should occur once every 28 days +/- 3 days for Cycle 2 onward. More frequent visits are permitted if clinically indicated.

While the following assessments will continue to be performed, they will only be done for clinical purposes. These data will no longer be entered into the study database:

- Physical examination
- ECOG performance status
- Vital signs (weight, temperature, blood pressure, respiration, pulse)
- Hematology and Chemistry per tables 6 and 7 that follow:

Table 6. Hematology Laboratory Tests

Basophils	Mean corpuscular volume
Eosinophils	Monocytes
Hematocrit	Neutrophils
Hemoglobin	Platelet count
Lymphocytes	Red blood cell count
Mean corpuscular hemoglobin	Total white cell count
Mean corpuscular hemoglobin concentration	

Table 7. Clinical chemistry (Serum or Plasma) Laboratory Tests

Albumin	Glucose
Alanine aminotransferase	Thyroid stimulating hormone (TSH), free triiodothyronine (T3), and free thyroxine (T4) (combination arm only)
	Magnesium
Aspartate aminotransferase	Potassium
Bicarbonate	Sodium
Calcium	Total bilirubin ^a
Chloride	Total protein
Creatinine	Urea or blood urea nitrogen, depending on local practice

^a If Total bilirubin is $\geq 2 \times \text{ULN}$ (and no evidence of Gilbert's syndrome) then fractionate into direct and indirect bilirubin

See Appendix G for additional laboratory requirements for Korean sites only.

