4.6 Biological sampling procedures

The volume of blood that will be drawn from each subject in this study is as follows:

Table 8: Volume of blood to be drawn from each subject

Assessment		Sample volume (mL)	Frequency of Sampling	Total volume (mL)
Safety	Clinical chemistry	3	Once at the start of each cycle	18 (for 6 cycles)
	Hematology	3	Once at the start of each cycle	18 (for 6 cycles)
Biomarker		30	At predefined time points	120 (4 time points)

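### Pregnancy is tested only at screening, so the rules that stop treatment for pregnancy have no scheduled on-treatment test to trigger them

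*Combined protocol and SAP*

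**What the plan says.** In Appendix A the row "Pregnancy test ^k" is marked in the Screening column and nowhere else. Footnote k says who is tested ("For women of childbearing potential (including those who have had a tubal ligation") and adds no repeat.

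Olaparib is "taken continuously in 28 day cycles". Section 3.1 sets no fixed number of cycles: "Study treatment will continue until disease progression, intolerable toxicity, elective withdrawal from the study, or study completion or termination". From Cycle 2, "Subsequent visits with study doctor should occur once every 28 days +/- 3 days for Cycle 2 onward", and Table 8 in 4.6 has chemistry and hematology blood drawn "Once at the start of each cycle".

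On risk, 1.1.3 reports reduced fetal survival and more fetal malformations in preclinical studies, and regards both as expected from the drug's pharmacology. Section 3.6.1 warns that olaparib may make hormonal contraceptives less effective. Every hormonal method listed under that warning is paired with a male condom and spermicide.

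On action, 4.3 lists a beta-hCG result consistent with pregnancy among the reasons for mandatory withdrawal from treatment, and 5.12.1 requires the study drugs to be stopped at once if a subject becomes pregnant.

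**The concern.** The plan has two stopping rules for pregnancy and a stated fetal hazard, but after screening it schedules nothing that would reveal a pregnancy. A pregnancy on treatment would come to light through the subject's report, the physician's suspicion, or an incidental finding on examination or scan. Until then olaparib, with durvalumab in the combination arm, could continue into early gestation. At stake is the length of fetal exposure before the rules in 4.3 and 5.12.1 are applied. Sample size and the PFS analysis are not affected.

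**Working it through.** The plan gives no figure on this point, so there is none to reproduce. The check is a reading of every place where a test could be scheduled, followed by a rough sizing.

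| Place | Pregnancy or hCG test |
|---|---|
| 3.4, criterion 13 | Negative test at the screening visit |
| 4.1.2 | Listed, screening |
| 4.5.1, Cycle 1 Day 1 | None |
| 4.5.2 with Tables 6 and 7 | None |
| 4.5.3, end of study visit | None |
| 4.7, follow-up | None |
| Appendix A | Screening only |
| Appendix G, Korean sites | None |

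In Appendix A the hematology, chemistry, liver and GFR rows are all marked again at Cycle 1, Cycle 2 onwards and End of treatment. The pregnancy row is the one safety laboratory row that stops at screening.

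One general rule could add a test: "Where laboratory investigations have not been performed within the 7-day period prior to starting treatment, they must be repeated" on Day 1 of Cycle 1 (4.1.2). At most this gives one further test, before the first dose. Appendix A leaves the pregnancy row blank in that column, so it is not clear that the rule applies.

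**Inputs.** From the documents: a failure rate of 1% per year, the ceiling for one highly effective contraceptive method (3.6.1, item 5), and median PFS of 2 months (null) or 4 months (alternative) from 7.1. Assumed: 20 to 40 of the 60 subjects are of childbearing potential; treatment time follows the exponential PFS distribution; the combination half stays on treatment 28 to 56 days beyond first progression while progression is confirmed (4.2.5, 4.8); a false-positive rate of 0.1% to 1% per test.

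**Expected pregnancies.** Mean treatment time = median / ln 2, which is 2.89 months (0.240 years) or 5.77 months (0.481 years). Expected number = subjects × years × 0.01:

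- 2-month median: 20 × 0.240 × 0.01 = 0.048; 40 × 0.240 × 0.01 = 0.096
- 4-month median: 20 × 0.481 × 0.01 = 0.096; 40 × 0.481 × 0.01 = 0.192
- With the extra time: 0.048 + 10 × (28/365.25) × 0.01 = 0.056, up to 0.192 + 20 × (56/365.25) × 0.01 = 0.223

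**Tests added.** Expected cycle starts per subject = 1 / (1 − exp(−28 × ln 2 / (median × 30.44))), which is 3.663 or 6.787. Dropping the Cycle 1 start and adding one test at End of treatment leaves the same count per subject:

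- 20 × 3.663 = 73, up to 40 × 6.787 = 271
- If every subject also needed a Cycle 1 Day 1 test: 73 + 20 = 93, up to 271 + 40 = 311
- The extra combination-arm time adds 10 × 1 = 10 to 20 × 2 = 40 tests to either range

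**False positives.** 73 × 0.001 = 0.07, up to 271 × 0.01 = 2.7 (311 × 0.01 = 3.1 with Cycle 1 Day 1 for all).

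**Per subject-year on treatment,** with no assumption about numbers of subjects: 0.01 expected pregnancies and 365.25/28 = 13.0 tests. This is the useful scale for the Extension period, whose size is not given.

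**The case against.** The best case against is that this is a matter of preference. No text requires on-treatment tests, and the rules in 4.3 and 5.12.1 work whenever a pregnancy becomes known. Contraception is demanding: 3.6.1 item 1 asks for two highly effective methods plus partner condom and spermicide (the later contraception list counts the condom as one of the two). Table 1 also offers a copper device, which the hormonal warning does not touch. A physician sees each subject about every 28 days, scans every 8 weeks include the pelvis, and section 4 allows extra tests when clinically indicated. Expected false positives may outnumber true pregnancies. Much of the whole-trial exposure may also be past, since the text has been revised for an Extension period.

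Most of this stands as to frequency. It does not close the gap: contraception lowers the risk but does not detect its failure, extra tests need a prior suspicion, and examinations and scans are not pregnancy tests. The false positives are a reason for a confirmation step.

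Four stronger readings are tempting, and the documents do not support them:

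- *Pregnancies on treatment are likely.* The expectation is well below one, at a rate for a single method when two are required.
- *The hormonal warning leaves subjects unprotected.* Each hormonal method listed there comes with condom plus spermicide, although item 5 does not rate condoms as highly effective.
- *Every subject needs a further test at Cycle 1 Day 1.* Appendix A puts screening within 14 days of that visit, and the 7-day rule may already cover the test.
- *Testing each cycle would guarantee detection within 28 days.* Appendix A says "Study assessments may be delayed or moved ahead of the window to accommodate holidays, vacations and unforeseen delays", so there is no guaranteed maximum gap.

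**Conclusion.** The point holds as a low-cost safety improvement. One pregnancy test is scheduled, at screening, and none during continuous, open-ended dosing with a drug whose fetal toxicity the protocol itself reports. The two pregnancy stopping rules therefore lack a scheduled trigger, and detection may be delayed. By how much cannot be estimated from the documents.

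Expected pregnancies are about 0.05 to 0.19 over the whole trial, or 0.06 to 0.22 with treatment past first progression. These are not bounds: two methods, toxicity stops and withdrawals lower them, and longer treatment raises them. They rest on the 1% rate, the protocol's medians and an assumed 20 to 40 subjects of childbearing potential. The argument is severity against very low cost, not frequency.

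**What to change.** For subjects of childbearing potential:

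- Mark the Appendix A pregnancy-test row at Day 1 of Cycle 2 onwards and at End of treatment, and add the test to 4.5.2 and 4.5.3. Use urine, or the blood already drawn each cycle. The clinical team may adjust the interval.
- Require a test at Cycle 1 Day 1 only if the screening test is more than 7 days old.
- Extend the confirmation rule in criterion 13 beyond screening: a positive or unclear urine result goes to a serum test, with study drug held meanwhile, before the 4.3 withdrawal applies. Say expressly that this hold is allowed, because 4.2.4 frames olaparib interruptions around toxicity.
- State one definition of childbearing potential for this row. Footnote k includes women with a tubal ligation, while 3.6.1 item 4 treats bilateral tubal ligation as surgical sterility.

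Results can stay in source records, as other Extension-period laboratory results do; a confirmed pregnancy is reported under 5.12.1.

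The cost is one schedule row, two visit-list lines and a few sentences, with no added visit or invasive procedure. Under the assumptions above that is about 73 to 271 tests over the whole trial, more if Cycle 1 Day 1 tests or post-progression cycles are added, and fewer if only the Extension period is affected. The downside is a small test cost per cycle and occasional false positives with a brief hold.
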